## 4D. Study Procedures

(there are no other study protocols)

	Participant safety	
	procedures	
Research procedures	(all participants; required	Clinical intervention
(all participants)	by ethical obligations to	(SPI only)

		study participants)	
In jail	Screening	Mandatory reporting of	Study clinician* will visit
	Consent	severe SI to the jail	participant in jail to conduct
~4 weeks after	Baseline assessment	Emorgonov roforrol based	the initial SPI session
release	Post-release follow-up assessment (by phone	Emergency referral based on assessment responses	
1010430	[unless reincarcerated;	on assessment responses	
	if in residential facility		
	may be done by phone		
	or in person)		
First ~6		Emergency referral by	SPI phone calls (4 planned,
months after		SPI clinicians (who are	another 4 optional) within the
release		licensed) based on clinical	first week, and at 1 mo, 3 mo,
		judgment	and 6 mo after jail release
~16 weeks	Post-release follow-up	Emergency referral based	
after release	assessment (by phone	on assessment responses	
	[or in-person if in a		
	residential treatment		
	facility] unless		
~34 weeks	reincarcerated) Post-release follow-up	Emergency referral based	
after release	assessment (by phone	on assessment responses	
	[or in-person if in a		
	residential treatment		
	facility] unless		
	reincarcerated)		
~52 weeks	Post-release follow-up	Emergency referral based	
after release	assessment (by phone	on assessment responses	
	[or in-person if in a residential treatment		
	facility] unless reincarcerated)		
I .	Tomodrocrated		

\*Study clinicians will be moonlighting for our study. To the extent possible, they will be drawn from the community mental health agencies (mental health and substance use services to re-entering individuals in each community.

In addition, we will also be collecting the following non-self-report data:

- Costs to us of providing the treatment
- Facility and community mental health budget information to allow us to project potential costs to them, as well as cost-savings
- Participant hospitalization and other medical records from local area hospitals and emergency rooms
- National death records
- Participant jail medical records (to compare our suicide screening results against the jail's)

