#### 9. Outcome Measures

Assessments will take place at baseline, and at 4, 16, 34, and 52 weeks post-release. Baseline assessments (including informed consent, locator, and release of information paperwork) will take place in person at the jail; RAs will offer to read each study assessment aloud. Follow-up assessments will take place by telephone (the most feasible way to do follow-ups with this population), unless a participant is reincarcerated, in which case the follow-up assessment will take place in person at the jail/prison. If a participant is in a residential treatment facility, the follow-up assessment may take place by phone or in person at the residential treatment facility.

Table C1: Assessments	Туре	Time (min)	Baseline	4, 16, 34, and 52 week Follow-up
Suicidal Ideation and Behavior				
Columbia Suicide Severity Rating Scale (C-SSRS) 181	Interview	20	X	X
L.I.F.E. 182 – suicidal ideation and behavior	Interview	10		X
Suicide deaths: record review (state/national death registry)	Objective	0		X
Hospitalizations: Tx History Interview, record review (local hospitals)	Objective	0	X	X
Psychiatric Symptoms:				
DSM-5 Cross-Cutting Measure	Self-Report	7	X	X
K6	Self-Report	1	X	X
LEC/PCL	Self-Report	7	X	X
AUDIT and DUDIT	Self-report	7	X	X
Overdose	Self-report	10	X	X
Functioning: VR-12  from RAND Medical Outcomes Study	Self-Report	3	X	X
Hypothesized Mechanisms				
Treatment utilization: Treatment History Interview 	Interview	8	X	X
Belongingness: Interpersonal Needs Questionnaire-12 	Self-Report	5	X	16 ,34, 52 only
Suicide-related problem-solving: Suicide Related Coping Measure	Self-Report	5	X	16, 34, 52 only
Diagnosis: Mini International Neuropsychiatric Interview (MINI)  : lifetime psychosis, mania/hypomania, major depressive episode	Interview	10		4 week only
Safety Plan use in the context of Substance Abuse	Interview	10		52 only
Total patient time for interview (min)			Consent[contact]

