Primary outcome. Suicide Events is a composite score consisting of the total number of occurrences of any of the following in the year after jail release: (a) attempted suicide (includes suicide deaths), (b) suicide behaviors (preparatory acts, aborted or interrupted suicide attempts), as defined using the Columbia criteria, 181,188 and (c) suicide-related hospitalizations. We will use the Treatment History Interview (THI189) as well as hospital records to track the number of subsequent hospitalizations and reasons for these admissions. Suicide event data will be assessed using data collected from all possible sources, including follow-up assessments (C-SSRS, THI), (b) hospital chart reviews, and (c) state/national registries. Data from all sources will be reviewed by 2 research team members for congruence. Disagreements will be reviewed and adjudicated by ... All reports will be classified using C-SSRS criteria. The C-SSRS is the recommended measure of suicidal ideation and behaviors in the NIH PhenX Toolkit as a core data element in all clinical trials for suicide prevention. Although it will not be included in our suicide event composite, we will also track implementation of rescue procedures (e.g. calling Emergency Services/police, breaking confidentiality to inform clinician of high suicide risk) during SPI phone calls or study assessments and compare conditions on this variable.

**Secondary outcomes.** Suicide Attempts. We will separately assess and evaluate total number of subsequent attempts using the procedures described above. Weeks of active suicidal ideation during the follow-up period will be operationalized using the Longitudinal Interval Follow-

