Sample descriptors will include baseline demographics. Study inclusion criteria are based on suicide risk rather than diagnosis, but we will gather some basic diagnostic information (lifetime psychosis, mania/hypomania, and major depression) using MINI modules (see Table). We chose the MINI to keep assessment interviews to 1 hour: keeping participant burden minimal (and hence, study procedures feasible and enrollment and follow-up rates high) was our primary consideration. We will administer the MINI modules at 4 week post-release because: (1) we are assessing lifetime diagnosis, and (2) giving it at the 4 week follow-up best balances the length of all assessments.

Hospital and death records. Most of is covered by 2 large health systems. is covered by 3 systems. As in ED-SAFE (a 7-state, 8-site trial is covered by 3 systems. As in ED-SAFE (a 7-state, 8-site trial is covered by 3 systems. As in ED-SAFE, 8-site trial is covered by 3 systems. See C3), we will obtain releases of information from participants at study intake to conduct chart reviews at all of the hospital systems in each region. As in ED-SAFE, RAs will review charts

following a structured protocol, utilizing discharge codes, discharge summaries, medications, laboratory results, operation records, nursing notes, physician progress notes and other notes or comments to determine whether a suicide event occurred. ED-SAFE data showed that this approach is feasible and that it enhanced detection of suicide events over and above telephone follow-up assessment, uniquely identifying 43% of the 1871 detected suicide-related events. Thus, a combination of records review with phone assessment is a feasible and robust approach to detecting suicide-related events. We will also search the National Death Index for ICD-coded suicide deaths in our sample.

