Cost-effectiveness measures. Our grant accounting will capture the costs of the SPI providers. We will also track treatment received as part of SOC for the SPI plus SOC and SOC conditions. SOC (including outpatient, inpatient, and ED mental health and suicide-related medical care visits) will be tracked using the THI, and costs of SOC will be estimated using costs for similar visits to SPI providers and charge data from state hospital and ED data systems adjusted to costs with facility-specific cost-to-charge ratios obtained from Federal cost reports. We will include training costs but exclude other research costs that would not be incurred if SPI were standard care. The primary cost-effectiveness (CE) measure will be the sum of suicide-related hospitalizations and medically treated and fatal suicide acts. Our secondary CE measure will be the SF-12. Our prior work found that Sengupta's HUI3 scoring was the best of 50 scorings of the SF-12. That scoring measures functional status in quality-adjusted life years (QALYs). Costs (and savings) in future years will be discounted to present value in the year of treatment initiation using the 3% discount rate recommended by the Panel on Cost-Effectiveness in Health and Medicine. Costs, benefits will be converted to same-year dollars.

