**Mechanisms of intervention effects.** We will separately test the hypotheses that, relative to SOC alone, SPI + SOC will result in more treatment utilization (number of outpatient mental health and substance use visits as assessed by the THI), more sense of belongingness (INQ-12 Belongingness Scale score), and better suicide-related problem solving (as assessed by the safety behavior checklist), our proposed primary and exploratory mechanisms, using Mplus, which can accommodate both standard and Poisson-class regression methods. We will then test the hypothesis that treatment utilization, suicide-related problem-solving skills, and belongingness (1) predict suicide events, and (2) mediate the effects of SPI on suicide events in a structural equation model framework to decompose total effects into direct and specific indirect effects. As recommended by MacKinnon et al, the statistical significance of the indirect effect will be assessed using bias-corrected bootstrapped standard errors; 95% CI estimates will be provided.

**Predictors/Personalization**. We will explore gender, race/ethnicity, lifetime suicide attempts, lifetime highest C-SSRS SI intensity score, severe mental illness (schizophrenia, bipolar disorder), substance use, and # of lifetime arrests as moderators. We expect that SPI is appropriate for a full range of at-risk jail detainees.

Cost-effectiveness analyses. We propose a comparative cost effectiveness (CE) analysis of SPI + SOC relative to SOC. The primary effectiveness measure is the sum of suicide-related hospitalizations and medically treated and fatal suicide acts, with a secondary measure of QALYs (see D2.12). Following widely accepted CE analysis guidelines, analyses will adopt a societal perspective, considering all economic costs regardless of source. If direct cost savings exceed the program costs, the program is said to offer net cost savings. We describe our statistical plan for determining mean change in and standard deviations of these measures above. The CE ratio equals  $\Delta C/\Delta E$ , where  $\Delta C$  is the difference in costs between SPI + SOC and SOC alone and  $\Delta E$  is the difference in the outcome measure. Using the Crystal Ball add-in to Excel, we will bootstrap 95% confidence intervals around the CE ratio and calculate a cost-effectiveness acceptability curve. Sensitivity analysis will examine CE ratios at 0%, 1% and 5% discount rates.

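### The cost side names only the Treatment History Interview for inpatient and ED use, while the effect side's components also come from hospital and death records, so as written the cost difference is incomplete

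*Combined protocol and SAP*

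**What the plan says.** Under cost-effectiveness measures, Section 9 says that "SOC (including outpatient, inpatient, and ED mental health and suicide-related medical care visits) will be tracked using the THI". The same sentence prices the visits, partly from "charge data from state hospital and ED data systems adjusted to costs with facility-specific cost-to-charge ratios". That clause supplies unit costs; it does not say that the state systems count visits. The paragraph then defines the effect: "The primary cost-effectiveness (CE) measure will be the sum of suicide-related hospitalizations and medically treated and fatal suicide acts". It does not restate where those counts come from.

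Other parts of the plan use two sources for hospitalizations. The primary-outcome paragraph of Section 9 uses the THI "as well as hospital records to track the number of subsequent hospitalizations and reasons for these admissions", and draws suicide events from interviews, chart review and death registries. Table C1 lists hospitalizations under both the THI and local record review. Section 4D lists "Participant hospitalization and other medical records from local area hospitals and emergency rooms" among the data to be collected, with no link to costing. The paragraph on hospital and death records justifies chart review by an earlier emergency-department trial, where it added to telephone follow-up, "uniquely identifying 43% of the 1871 detected suicide-related events".

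Section 10A defines the ratio as the cost difference over the effect difference, takes a societal perspective, and adds: "If direct cost savings exceed the program costs, the program is said to offer net cost savings".

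**The concern.** The numerator and denominator of the ratio would rest on different sets of events. An admission that the participant does not report, but the chart shows, is an event in the denominator and costs nothing in the numerator. The same holds for the terminal care of someone who dies before the next interview, and for hospital care of anyone never interviewed after release.

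At stake are the cost per event averted and the net-savings statement. Both depend on hospital costs offsetting program costs, and cost-effectiveness is part of the trial's stated objective (Section 2). An analysis meant to cover all economic costs should not omit stays that the study itself has found.

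**Working it through.** **The plan's own figures.** The documents state no cost or cost-effectiveness figure to reproduce. The hospitalization rates below come from the power calculation in Section 10B. Using its rates with 312 per arm (78% of 800, halved), a latent correlation of 0.5, a rank test with ties and 4,000 simulated trials gives 95.9% power against the stated 96.5%. The rates are therefore read as intended. The evaluable share also reproduces: 0.85 × 0.92 = 78.2%.

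**Inputs.**
- Hospitalization: 12% control, 7% intervention (Section 10B). These are proportions of people with any hospitalization, so one admission per hospitalized person is assumed.
- THI capture, the share of admissions it records: s0 in control, s1 in intervention. The plan gives no value. One reference point is 1 − 0.43 = 0.57, from suicide-related events in the earlier trial; the rest of the range is assumed.
- Interview coverage (Section 10B): 92% released, 85% of those with at least one follow-up interview, 70% interviewed at 52 weeks.

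**Coverage.** Released: 0.92 × 800 = 736. No post-release THI: 0.15 × 736 ≈ 110. No 52-week interview: 0.30 × 736 ≈ 221; no later study interview can recover what those people would have reported there. Section 10B promises medical and death records for all released participants, and Section 4C seeks permission for records even from those who refuse interviews.

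**Equal capture (s0 = s1 = s).** Difference in admissions per 100 = 12 − 7 = 5. Costed difference = 5 × s. Understatement = 1 − s.

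| THI capture | Costed difference per 100 | Understated by |
|---|---|---|
| 57% | 2.85 | 43% |
| 70% | 3.5 | 30% |
| 80% | 4.0 | 20% |
| 90% | 4.5 | 10% |
| 100% | 5.0 | 0% |

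With 312 per arm, 0.05 × 312 = 15.6 admissions are averted. At 57% capture, 15.6 × 0.57 = 8.9 are costed and 6.7 are not.

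**Unequal capture.** Costed difference per 100 = 12 × s0 − 7 × s1.
- s0 = 0.57, s1 = 0.67: 6.84 − 4.69 = 2.15, a larger understatement.
- s0 = 0.57, s1 = 0.47: 6.84 − 3.29 = 3.55, a smaller one.
- The saving is overstated once s1 falls below (0.12 × s0 − 0.05) / 0.07. That threshold is about 26% when s0 = 57%, 49% when s0 = 70%, 66% when s0 = 80% and 83% when s0 = 90%.

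At high capture, then, a modest gap between arms is enough to reverse the direction.

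**The case against.** The cost paragraph names the THI but does not say that records are excluded, and it does not state the source of the effect counts. The authors may have meant the two-source hospitalization count to serve both purposes. A reader might infer that the plan deliberately costs charted admissions at zero; the text does not go that far. What stands is that a concrete method is stated, it names one source where the plan elsewhere names two, and nothing links the records to costs. On the effect side, fatal acts at least cannot come from an interview.

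A reader might also infer that savings are bound to be understated. That requires the intervention to reduce admissions and capture to be similar by arm, and neither is established. Intervention clinicians can refer to the ED (Sections 1H and 8C), so hospital use could rise; the same gap would then hide added cost and favor the intervention.

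The 43% might be taken as the size of the error. It describes suicide-related events in another population, not admissions missed by the THI among released detainees.

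Finally, Section 10A collects missed self-report counts at later interviews and plans multiple imputation and an extreme-value sensitivity analysis. These partly cover missed interviews. They do not restore a stay left unreported in a completed interview.

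**Conclusion.** The concern holds as an inconsistency in ascertainment that should be corrected, with a conditional direction. As written, the cost difference omits suicide-related hospital care known only from records, while the effect difference, read with the rest of Section 9, includes it. With 12% versus 7% hospitalized, one admission per person and equal capture, the costed saving is understated by 10% at 90% capture and 43% at 57%, and not at all at full capture. Higher hospital use under the intervention, or sufficiently lower capture in that arm, would turn the bias in the intervention's favor.

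Whether the net-savings statement would change cannot be computed, because the plan gives neither program cost nor cost per admission. The primary outcome and its test are not affected.

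**What to change.** In the cost-effectiveness paragraph of Section 9, state that suicide-related inpatient stays and ED visits are costed from the same reconciled THI-plus-records list that supplies the effect measure. Keep one record per stay, matched by date, and include participants who died or were not interviewed. Keep the THI for outpatient visits and for mental health stays that the chart review does not abstract. Handle missing THI outpatient costs of non-interviewed participants with the planned multiple imputation, so that their totals are not hospital cost alone. If the common list was always intended, saying so is enough.

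The cost is modest. Charts are already being reviewed to detect suicide events, but admission and discharge dates must be kept and matched to the THI. Chart review covers regional hospital systems only, so stays elsewhere still depend on the interview. That is why the list should combine both sources rather than replace one with the other.

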## 10. Statistical Analysis

## 10A. Data Analysis

Primary analyses will be *intent-to-treat;* we will examine dose-response effects in secondary analyses. Primary tests will be 2-sided with  $\alpha$ =0.05. Site differences will be modeled with fixed effects. Descriptive statistics will include effect sizes and measures of clinical significance (i.e., area under the curve; number needed to treat) for all major comparisons. We will separate primary hypothesis (Aim 1) from remaining hypotheses (Aims 2-4). Standard post hoc procedures will be used to adjust for multiple comparisons when testing secondary hypotheses. There is no planned interim analysis. Analyses will adjust for baseline levels of dependent variables, gender, and yes/no history of suicide attempts. Consistent with CONSORT guidelines, we will pre-specify covariates and will not adjust for imbalance observed post hoc.

The original grant application stated that: "We will finalize and total data from each study phase that has been completed as they are completed (i.e., intake and 1-month follow-up will be complete by Month 32, 4-month follow-up will be complete by Month 35, 8-month follow-up will be complete by Month 39, and 12-month will be complete by Month 43). Given the timelines for data cleaning and recoding described above, intake and 1-month follow-up data will be available for analysis by Month 32, 4-month follow-up will be available for analysis by Month 35, 8-month follow-up data will be available for analysis by Month 39, and 12-month data will be available for analysis by the end of Month 43." Our timeline slid a little from this proposal due to recruiting another 3 months and waiting to see if anyone else would get out of jail. At this point, per the original analysis plan, we will close the assessment windows and begin data analysis for each wave as follows:

- Baseline: 4/12/19
- 4-week: 4/12/19 (all participants will be at least 4-weeks from their release date at this point)
- 16-week: 5/12/19 (all participants will be at least 16-weeks from their release date by this date)
- 34-week: 9/12/19 (all participants will be at least 34-weeks from their release date by this date)
- 52-week: 1/20/20 (all participants will be 52-weeks from their release date by this date)

**Missing Data.** We will collect medical record and death record data on all participants. Self-reported count (e.g., suicide events) and historical (e.g., weekly LIFE ratings) data from missed assessments will be gathered at later follow-up assessments. We will use multiple imputation to deal with missing data. We will compare treatment conditions on rates of missingness and time to missingness and will test whether baseline characteristics are associated with missingness. Finally, we will perform a sensitivity analysis in which we impute extreme values for missing data to determine the sensitivity of analysis results to missing data.

**Outcomes.** Primary. We will test the hypothesis that, relative to SOC alone, SPI + SOC will result in fewer suicide events over the 52 week follow-up period, using ordinal logistic regression with lifetime suicide attempts events at baseline as a covariate. The analysis framework will be multivariate ordinal dependent variable regression. We begin with ordinal models because our simulations suggest the count outcome will not likely exceed 3. We will explore using different models such as zero-inflated Poisson or zero-inflated negative binomial with an offset defined by the length of follow-up and time in the community (as opposed to reincarcerated), and other reasonable approaches. Determination of the appropriate modeling will be determined using model selection (information) criteria and the determination will be made blind to the effect of the SIP intervention. Secondary. We will separately test the hypotheses that, relative to SOC alone, SPI + SOC will result in fewer suicide attempts, fewer weeks of active suicide ideation (per the LIFE calendar), lower severity of suicide ideation (C-

SSRS scores), longer time to first suicide event, fewer psychiatric symptoms (DSM-5 Cross Cutting Measure scores), and better psychosocial functioning (SF-12 scores). For normally distributed variables (i.e., C-SSRS, DSM-5 Cross Cutting, SF-12, AUDIT, DAST-10), analyses will use a generalized linear mixed model framework for multilevel data (e.g., SAS/proc mixed, HLM) with baseline scores as covariates. For count data (i.e., number of suicide attempts, weeks of active suicide ideation), analyses will use Poisson-class regression methods 204,205 (e.g., negative binomial regression) and will include appropriate tests for zero-inflation and overdispersion and offset defined by length of time of follow-up and time in the community. Time to suicide event will be analyzed using time-to-event models, beginning with semi-parametric Cox regression models assuming proportionality assumptions are met, otherwise discrete time or parametric continuous time survival models will be used. Model choice will be informed by information criteria and decisions made blind to intervention assignment. Exploratory, Although not part of formal hypotheses, we will also compare conditions on (1) rates of death by suicide, (2) number of re-arrests, and (3) number of emergency referrals generated as part of study assessment safety procedures. Supplement. We will examine whether SPI+SOC has a differential effect on overdose rates and on overdose versus non-overdose suicide attempts. Qualitative data also will be collected at the end of the 12-month follow-up interview to better understand how individuals used or did not use their Safety Plan in the context of substance abuse.

**Mechanisms of intervention effects.** We will separately test the hypotheses that, relative to SOC alone, SPI + SOC will result in more treatment utilization (number of outpatient mental health and substance use visits as assessed by the THI), more sense of belongingness (INQ-12 Belongingness Scale score), and better suicide-related problem solving (as assessed by the safety behavior checklist), our proposed primary and exploratory mechanisms, using Mplus, which can accommodate both standard and Poisson-class regression methods. We will then test the hypothesis that treatment utilization, suicide-related problem-solving skills, and belongingness (1) predict suicide events, and (2) mediate the effects of SPI on suicide events in a structural equation model framework to decompose total effects into direct and specific indirect effects. As recommended by MacKinnon et al, the statistical significance of the indirect effect will be assessed using bias-corrected bootstrapped standard errors; 95% CI estimates will be provided.

**Predictors/Personalization**. We will explore gender, race/ethnicity, lifetime suicide attempts, lifetime highest C-SSRS SI intensity score, severe mental illness (schizophrenia, bipolar disorder), substance use, and # of lifetime arrests as moderators. We expect that SPI is appropriate for a full range of at-risk jail detainees.

Cost-effectiveness analyses. We propose a comparative cost effectiveness (CE) analysis of SPI + SOC relative to SOC. The primary effectiveness measure is the sum of suicide-related hospitalizations and medically treated and fatal suicide acts, with a secondary measure of QALYs (see D2.12). Following widely accepted CE analysis guidelines, analyses will adopt a societal perspective, considering all economic costs regardless of source. If direct cost savings exceed the program costs, the program is said to offer net cost savings. We describe our statistical plan for determining mean change in and standard deviations of these measures above. The CE ratio equals  $\Delta C/\Delta E$ , where  $\Delta C$  is the difference in costs between SPI + SOC and SOC alone and  $\Delta E$  is the difference in the outcome measure. Using the Crystal Ball add-in to Excel, we will bootstrap 95% confidence intervals around the CE ratio and calculate a cost-effectiveness acceptability curve. Sensitivity analysis will examine CE ratios at 0%, 1% and 5% discount rates.

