Up Evaluation (LIFE;190). At each assessment point, we will ask participants to rate their level of suicidal ideation in the weeks since the last assessment on a 6-point psychiatric status rating scale. This LIFE method yields weekly scores and allows us to examine both the occurrence and chronicity of suicidal ideation over the follow-up period. The LIFE calendar will also be used to assess time to first suicide event. As in this study, the LIFE is often administered by phone (i.e. 191, 192). Severity of suicide ideation. We will also assess severity of suicidal ideation using the Suicidal Intensity subscale from the C-SSRS. Psychiatric symptoms will be assessed using the DSM-5 Level 1 Cross-Cutting Symptom Measure. This measure was chosen because it is the recommended measure of broad psychopathology in the Tier 1 Core for Mental Health research in the NIH PhenX Toolkit, performed well psychometrically in the DSM-5 Field Trials, and is comprehensive yet brief. Substance use will be measured using the Alcohol Use Disorders Identification Test (AUDIT) and the Drug Use Disorders Identification Test (DUDIT). These measures were chosen as they are well validated, brief measures that have been used in several countries and clinical settings, and are cross-referenced as relevant common data elements in the Suicide Specialty Collection of the NIH PhenX Toolkit. As part of the supplement, we also will assess Overdose through a series of questions asked during baseline and follow-up assessments. Overall functioning will be measured using the VR-12, 183 a brief, widely used measure of physical and mental health functioning that also provides our secondary costeffectiveness measure (see below).

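### Weeks of active suicidal ideation has no baseline measure of ideation to adjust for, and section 10A names no substitute although the C-SSRS is collected at baseline

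*Combined protocol and SAP*

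**What the plan says.** The opening paragraph of section 10A sets a general covariate rule: "Analyses will adjust for baseline levels of dependent variables, gender, and yes/no history of suicide attempts". It models site with fixed effects and adds that "we will pre-specify covariates and will not adjust for imbalance observed post hoc".

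Section 9 defines the outcome in question "during the follow-up period will be operationalized using the Longitudinal Interval" Follow-up Evaluation (LIFE). On how the ratings are obtained it says "we will ask participants to rate their level of suicidal ideation in the weeks since the last assessment". In Table C1 the row "L.I.F.E. 182 – suicidal ideation and behavior" is marked under the 4-, 16-, 34- and 52-week follow-ups and is empty under baseline. The row "Columbia Suicide Severity Rating Scale (C-SSRS) 181" is marked under both.

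For individual outcomes, 10A is uneven about baseline adjustment:

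- The primary ordinal model names lifetime suicide attempts or events at baseline.
- The outcomes treated as normally distributed, including the C-SSRS severity score, take their own baseline scores.
- The count outcomes ("number of suicide attempts, weeks of active suicide ideation") get Poisson-class regression, checks for zero-inflation and overdispersion, and an offset for follow-up and community time. No baseline covariate is named there.

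**The concern.** The general rule asks for a baseline level that, for weeks of active ideation, does not exist. The analyst must either leave baseline ideation out or choose a stand-in that the plan does not name. More than one is available: section 9 uses the C-SSRS Suicidal Intensity subscale for the severity outcome, while the moderator list in 10A uses a lifetime-highest intensity score.

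Baseline ideation should vary in this sample. Section 3B admits people on past-month ideation with intent, on a past-month attempt, or on both, so some may enter on the attempt alone. The covariates that remain for this outcome do not measure ideation. At stake are some precision, protection against chance imbalance in baseline ideation, and one avoidable analyst choice in a plan that commits to pre-specified covariates.

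**Working it through.** **1. Can the rule be met from the schedule?**

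| Item | Source | Content |
|---|---|---|
| Rule | 10A, opening paragraph | Adjust for the baseline level of the dependent variable; no exception stated |
| Outcome source | 9, secondary outcomes | LIFE only, over the follow-up period |
| LIFE schedule | Table C1 | Follow-up only |
| LIFE recall | 9 | Weeks since the previous assessment |
| Count-outcome model | 10A, secondary outcomes | No baseline covariate named |
| C-SSRS schedule | Table C1 | Baseline and every follow-up |

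Table C1 was read from PDF, so the empty LIFE cell could have been an extraction fault. The recall wording makes that unlikely: a rating that covers the time since the previous assessment needs a previous assessment. The baseline level therefore does not exist for this outcome. What remains is site, gender and attempt history.

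**2. The plan's own figure.** The plan gives no power for this outcome. Its one power figure, 96.5%, is for the primary outcome. A simulation on the stated inputs (4,000 replicates, 312 per arm, two-sided 5%, proportional-odds score test) gives 95.4% if the stated 0.50 is a latent correlation and 93.1% if it is a correlation between the binary components. The figure is broadly reproduced, and the present point does not change it.

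**3. Size of the possible gain.** Inputs:

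- Evaluable sample: 0.78 × 800 = 624, or 312 per arm (section 10B, 1:1 allocation).
- r, the correlation between the baseline C-SSRS intensity score and follow-up weeks of ideation: not in the documents, so assumed at 0.2 to 0.5.
- A true difference of 0.20 SD for the power column: also assumed.

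Formulas (normal approximation, two-sided 5%):

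- share of residual variance removed = r²
- equivalent sample-size multiple = 1/(1 − r²)
- minimum detectable difference at 80% power = (1.960 + 0.842) × √(2/312) × √(1 − r²), which at r = 0 is 2.802 × 0.0801 = 0.224 SD
- power at 0.20 SD = Φ(0.20 / [√(2/312) × √(1 − r²)] − 1.960)

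| r | Variance removed | Sample-size multiple | Detectable difference (SD) | Power at 0.20 SD |
|---|---|---|---|---|
| 0 (no ideation covariate) | 0% | 1.00 | 0.224 | 70.5% |
| 0.2 | 4% | 1.04 | 0.220 | 72.2% |
| 0.3 | 9% | 1.10 | 0.214 | 74.5% |
| 0.4 | 16% | 1.19 | 0.206 | 77.8% |
| 0.5 | 25% | 1.33 | 0.194 | 82.2% |

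Two features push towards the lower rows. The entry criteria restrict the range of baseline ideation. The outcome is a count for which 10A itself plans zero-inflation checks, and the linear approximation overstates the gain for such a count.

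**The case against.** The strongest reply is that 10A should be read as a whole. The general sentence does not say that it covers every outcome, and the later text attaches baseline scores to the normally distributed outcomes only. On that reading, baseline adjustment applies where a baseline level exists, and the model for weeks of ideation can be run as written. It can indeed be run. But 10A does not state this exception, and it leaves unused a baseline measure of the same construct.

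A second reply is that the data for a substitute may not exist, because the documents give no recall window for a baseline intensity score. The first part does not hold: the C-SSRS is scheduled at baseline, section 9 takes severity from its intensity subscale, and 10A uses the baseline score for that outcome. The missing window is a fair criticism and belongs in the fix.

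A third reply is that ideation already has a baseline-adjusted analysis, through severity. That is true and lowers the stakes. It does not adjust the separate outcome of weeks of ideation.

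Some stronger inferences are tempting and are not supported:

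- **That the outcome is unadjusted.** Site, gender and attempt history still apply.
- **That the plan forbids a substitute.** It rules out adjustment prompted by observed imbalance, not a covariate named in advance.
- **That baseline ideation is the best predictor, or that a gain at the upper end of the table should be expected.** No document gives a correlation.
- **That time to first suicide event needs the same covariate.** It too has no baseline level of its own, but the primary model adjusts for lifetime attempts or events at baseline. Giving the time-to-event version an ideation score would adjust two analyses of the same events differently, and nothing in the documents argues for that.

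**Conclusion.** The point holds as a narrow, low-severity one. For weeks of active suicidal ideation, the baseline rule in 10A cannot be met and no substitute is named, so no baseline measure of ideation enters the model although one is collected.

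The consequence is precision on one secondary outcome: about 4% to 25% of residual variance for an assumed r of 0.2 to 0.5 on a linear approximation, and less for a zero-heavy count. With a restricted baseline range, the lower part of that interval is the more cautious expectation. A reader might infer that the treatment comparison would be biased. The documents do not support that, because allocation is randomised and omitting a prognostic covariate does not by itself bias the comparison. The primary analysis names its own baseline covariate and is unaffected.

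**What to change.** Add one sentence to the secondary-outcomes paragraph of 10A: because the LIFE is not given at baseline, the model for weeks of active suicidal ideation will use as its baseline covariate the same baseline C-SSRS Suicidal Intensity score that is used for the severity-of-ideation outcome. State the recall window of that score, and how it is scored for a participant who enters on an attempt and reports no ideation in that window. Under Missing Data, list the score among the predictors in the multiple-imputation model, for which no predictors are given at present. Leave the covariates for time to first suicide event as they are.

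The sentence should be in place before outcome data are analysed by arm. The cost is a sentence in 10A, a line under Missing Data and one degree of freedom, with no new data collection.
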